9.4 OTHER ANALYSES

9.4.1 Safety Analyses

This study will utilize a Data and Safety Monitoring Board (DSMB) comprised of study personnel (the study PI, biostatistician, and ICU medical directors, [name]), as well as an independent medical monitor ([name], Chief of Division of Allergy, Immunology and Infectious Diseases at Robert Wood Johnson University Hospital). [name] has served on data safety and monitoring committees for multiple federally- and industry-funded clinical trials, many of which have involved the study of ventilator-associated pneumonia.

The DSMB will meet every two months to review the following safety metrics: 1) Mortality per 1000 mechanically-ventilated patient days per ICU, Ventilator- associated events (using Centers for Disease Control/National Healthcare Safety Network definitions) per 1000 mechanically-ventilated patient days per ICU, Median duration of mechanical ventilation per patient per ICU. All safety outcomes will be compared to preintervention ICU data collected over the last 5 years to ensure that postintervention values fall within 2 standard deviations of preintervention controls. The study will be halted if any safety outcome is increased by more than 2 standard deviations relative preintervention control data. If safety outcomes are decreased by more than 2 standard deviations relative to preintervention control data (i.e. in a favorable direction following the intervention), the study intervention will be continued as this is a single-arm study trial design.

9.4.2 Sub-Group Analyses

We will also perform a series of prespecified confirmatory subgroup analyses for all study outcomes, stratified by individual study ICU and DSI implementation phase (for the latter, in order to account for seasonality, outcomes in the post-intervention cohort were compared to historical control patients admitted to study ICUs during analogous months in the pre-intervention control period).

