1 PROTOCOL SUMMARY

1.1 SYNOPSIS

[figure not shown]
Title:	Implementation of a Diagnostic Stewardship Bundle for Ventilator-associated Pneumonia among Mechanically-ventilated patients: a pilot/feasibility trial.
Grant Number:	Not applicable
Study Description:	A pilot/feasibility trial to evaluate the safety and efficacy of a multi-faceted ventilator-associated pneumonia diagnostic stewardship bundle. Trial ICUs will sequentially implement interventions targeting the respiratory culture diagnostic testing pathway to minimize diagnostic error and overtreatment of ventilator-associated pneumonia.
Objectives:	
Primary Objective: To determine the safety of a multi-faceted ventilator-associated pneumonia diagnostic stewardship bundle.
 
Secondary Objectives:
 
- To determine the association between a multi-faceted ventilator-associated pneumonia diagnostic stewardship bundle and ICU antibiotic utilization rates.- To determine the association between a multi-faceted ventilator-associated pneumonia diagnostic stewardship bundle and rates of positive respiratory cultures.
Endpoints:	To assess study feasibility and adherence to protocolized intervention.
	
Primary Endpoints:
 
- Mortality per 1000 mechanically-ventilated patient days- Ventilator-associated events (using Centers for Disease Control/National Healthcare Safety Network definitions) per 1000 patient days- Median duration of mechanical ventilation per patient.
	
Secondary Endpoints:
 
- Positive respiratory cultures per 1000 mechanically-ventilated patient days.- Total ICU antibiotic utilization rates (total antibiotic days of therapy per 1000 mechanically-ventilated patient days).- Broad-spectrum ICU antibiotic utilization rates (broad-spectrum antibiotic days of therapy per 1000 mechanically-ventilated patient days).- Respiratory cultures ordered per 1000 patient days.- Percentage of respiratory cultures obtained by BAL.- Percentage of respiratory cultures from BAL samples with alveolar neutrophils <50% (for Phase 2 only)
Study Population:	All mechanically-ventilated patients hospitalized within Michigan Medicine Cardiac Care Unit (CCU) and Critical Care Medicine Unit (CCMU).

Phase or Stage:	Pilot/feasibility trial of a population-based intervention.
Description of Sites/Facilities Enrolling Participants:	2 Michigan Medicine Intensive Care units.

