5 STUDY DESIGN

5.1 OVERALL DESIGN

We plan to conduct a quasi-experimental, single-arm pilot/feasibility trial of a VAP diagnostic stewardship bundle in the MM Critical Care Medicine Unit (CCMU) and Cardiac Care Unit (CCU). This is a population-based rather than individual intervention. Both the CCMU and CCU will designate team leaders (one faculty member, fellow, and unit nurse), who will be instructed on study design and rationale, to disseminate study information and education in concert with study PI to colleagues through use of infographics and powerpoint-based sessions.

The study intervention will consist of interventions at all 3 phases of the diagnostic testing pathway (see Section 7 for full details). The bundle's first two interventions (ordering & collection phase interventions) will be implemented at the onset of the study period. The final bundled intervention (reporting phase) will be implemented 6 months after study onset (see Study Timeline (section 1.2)).

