9.1.2 Hypotheses

The primary study hypothesis was that implementation of a bundled DSI targeting the respiratory culturing pathway would not associate with significant increases in adverse safety outcomes.

The secondary study hypotheses were that implementation of a bundled DSI targeting the respiratory culturing pathway would associate with reductions in rates of respiratory culture positivity (RCP) and ICU-antimicrobial utilization rates (ICU-AURs).

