9.2 ANALYSIS OF THE PRIMARY AND SECONDARY ENDPOINT(S)

Primary and secondary study outcomes will be compared between patient cohorts before and after DSI implementation. All primary/secondary study outcomes will compare patients admitted to study ICUs over the course of the year-long study intervention (Feb 2022-23) versus those admitted in the pre-intervention historical control period (Feb 2017-22). As above, rate variables will be compared using a z-score test. A p-value of 0.05 will be utilized for statistical significance.

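### Section 9.4.2 calls the ICU and phase subgroup analyses of every outcome confirmatory, with no multiplicity control and no test of whether ICUs or phases differ

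*Combined protocol and SAP*

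**What the plan says.** Section 9.4.2 provides for "a series of prespecified confirmatory subgroup analyses for all study outcomes", "stratified by individual study ICU and DSI implementation phase". For the phase split, post-intervention patients are compared with historical patients from the same calendar months, to deal with seasonality.

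There are two strata on each factor. The synopsis gives the sites as "2 Michigan Medicine Intensive Care units". Section 5.1 starts the ordering and collection interventions at study onset and then says: "The final bundled intervention (reporting phase) will be implemented 6 months after study onset".

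On testing, section 9.2 says that "rate variables will be compared using a z-score test" and "A p-value of 0.05 will be utilized for statistical significance". That sentence concerns the primary and secondary comparisons; section 9.4.2 gives no threshold of its own. Sections 9.1 to 9.4 mention no alpha split, ordering of tests or adjustment, and no interaction of period with ICU or phase. The one interaction in the plan, in section 9.3, concerns the time trend before and after the intervention.

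The synopsis and section 2.2 describe a pilot/feasibility study that gathers early data on efficacy and safety.

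**The concern.** *Confirmatory* tells the reader that a significant result may be taken as established, with the error rate controlled. Nothing in section 9 provides that control, and the label sits oddly with a pilot. It also reverses the usual weighting of evidence. The time-series and covariate-adjusted analyses, which address trend and confounding, are headed exploratory in section 9.3, while stratum comparisons with no stated adjustment beyond month matching are called confirmatory.

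Two misreadings follow. A chance p<0.05 in one ICU or phase could be reported as a confirmed effect there. And significance in one stratum but not the other could be read as a difference between strata, which the plan never tests.

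The safety outcomes carry a further risk in the opposite direction. The primary hypothesis is that the bundle "would not associate with significant increases in adverse safety outcomes". A stratum holds only part of the data, so a non-significant result there is easy to obtain, and under a confirmatory label it could be taken as confirmed safety.

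**Working it through.** The plan states no familywise error rate or number of tests, so there is no figure of its own to reproduce.

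**Inputs from the documents**
- Outcomes: nine in the synopsis, three primary (safety) and six secondary. The BAL neutrophil percentage is marked there as Phase 2 only, which leaves eight with a natural before/after comparison in every stratum. The hypotheses in section 9.1.2 cover six: the three safety outcomes, positive cultures, total antibiotic use and broad-spectrum antibiotic use.
- Strata: 2 ICUs + 2 phases = 4.
- Threshold: 0.05, carried over from section 9.2.

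**Assumptions**
- Tests are two-sided (sidedness is not stated) and each has its nominal size.
- For the dependent case, the four ICU-by-phase cells are of equal size and all pairs of outcomes share a correlation ρ. The documents give no value, so a range is shown.

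**Number of tests:** 6 × 4 = 24; 8 × 4 = 32; 9 × 4 = 36.

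**Independent tests, every null true:** P(at least one p<0.05) = 1 − 0.95^k.
- k = 24: 1 − 0.95^24 = 70.8%
- k = 32: 1 − 0.95^32 = 80.6%
- k = 36: 1 − 0.95^36 = 84.2%

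**Only the three safety outcomes null:** 3 × 4 = 12 tests; 1 − 0.95^12 = 46.0%.

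**False benefit only, on the three hypothesised efficacy endpoints:** 12 tests at 0.025 in the favourable direction; 1 − 0.975^12 = 26.2%.

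**Allowing for dependence.** The ICU and phase strata divide the same patients in two ways, and the outcomes are related. A simulation of 200,000 runs with overlapping strata gives:

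| Null tests | Independent | ρ = 0 | ρ = 0.3 | ρ = 0.5 | ρ = 0.7 | ρ = 0.9 |
|---|---|---|---|---|---|---|
| 24 | 70.8% | 65.0% | 60.8% | 54.3% | 45.0% | 31.8% |
| 32 | 80.6% | 75.5% | 70.3% | 62.0% | 50.4% | 34.2% |
| 36 | 84.2% | 79.5% | 73.7% | 65.3% | 52.7% | 35.3% |
| 12, safety only | 46.0% | 40.9% | 39.4% | 36.3% | 32.2% | 25.5% |
| 12, efficacy, benefit only | 26.2% | 22.6% | 20.9% | 19.0% | 16.7% | 13.1% |

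The columns from ρ = 0 onward include the stratum overlap. The last row should be set against 2.5% for a single test in one direction, the others against 5%. Even with nine almost identical outcomes (ρ = 0.999), the four strata alone keep the either-direction figure at 17.7%.

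Per-test error could exceed 0.05 if the rates are overdispersed, for example because antibiotic days cluster within patients. The documents give no data from which to size this.

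**The case against.** The best defence is that the label is loose wording. The subgroups sit under other analyses in section 9.4, in a declared pilot, and may be meant as checks that the main result is consistent across strata. No decision hangs on their p-values: the halting rule in section 9.4.1 uses a two-standard-deviation limit, and section 4 ties any rethinking before a multicentre study to adherence. This limits the consequence, and the documents do not support a claim that subgroup p-values will steer the next trial. It does not rescue the word, which asserts an inferential status that the plan does not provide.

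A reader might also infer that a false confirmed effect is likely, at 84%. That needs 36 independent tests with every null true. Thirty-six counts a Phase 2-only endpoint in every stratum. Cultures ordered and the percentage obtained by BAL are acted on directly by the order set, so a null there is implausible. Total and broad-spectrum antibiotic use overlap, as do cultures ordered and positive cultures. With only the safety outcomes null, or counting only false efficacy benefits, no figure reaches 50%. This part of the objection stands.

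A third tempting step is to demand a multiplicity correction, including for a Phase 2 safety claim. Bonferroni over 32 tests would set the threshold at 0.05/32 = 0.0016. Because the hypothesis is no significant increase, a stricter threshold makes harm harder to detect and an apparent finding of safety easier to reach.

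Finally, nothing shows that the strata are small in absolute terms: no sample size is given, and one year is compared with five in two whole ICUs. What can be said is that each stratum has less information than the whole study.

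**Conclusion.** The concern holds as a mislabelling with a real inferential consequence. Section 9.4.2 claims confirmatory status for subgroup tests of every outcome, with no error control and no test of whether strata differ.

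For 24-36 tests under the global null, the chance of at least one p<0.05 is 71-84% if independent, and about 45-80% with overlapping strata and outcome correlation of 0 to 0.7. It is about 32-46% if only the safety outcomes are null, and about 17-26% for a false benefit on the three hypothesised efficacy endpoints. At a correlation of 0.9 the figures are lower still, but all remain well above the single-test rate.

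These sizes rest on 0.05 applying in section 9.4.2, on two-sided tests of nominal size, on equal cells and on assumed correlations. That a false confirmed effect is more likely than not is not established; that the error rate is far from controlled is. The plan should be amended, and the amendment is small.

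**What to change.** In section 9.4.2:

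- Replace *confirmatory* with *exploratory*.
- Report each stratum's estimate with a 95% interval and make no significance claims. The Phase 2-only neutrophil endpoint can be described without a before/after test.
- State that a non-significant safety result in a stratum is not evidence of safety; the upper end of the interval shows what increase remains compatible with the data.
- Assess ICU differences with a period-by-ICU interaction.
- Assess phase differences with a contrast of the two before/after effects, each against its own month-matched controls. A plain phase term would mix phase with season. For rates, this is the Phase 2 log rate ratio minus the Phase 1 log rate ratio, with its interval.
- Do not add an alpha adjustment for subgroup safety outcomes.

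The cost is a few lines of text and two added contrasts per outcome that has a before/after comparison. The real downside is that fewer claims can be made from the subgroups, and the interaction estimates will be less precise than the overall comparison.

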10 SUPPORTING DOCUMENTATION AND OPERATIONAL CONSIDERATIONS

10.1 CONFIDENTIALITY AND PRIVACY

10.1.1 Data sharing

Sharing of data generated by this project is an essential part of our proposed activities and will be carried out in several different ways. We would wish to make our results available both to the community of scientists interested in ventilator-associated pneumonia to avoid unintentional

duplication of research. Conversely, we would welcome collaboration with others who could make use of protocols developed in this project. Data generated from this projects will be shared at national meetings and conferences and in peer-reviewed publications.

We will share the final data in accordance with NIH policy. The final dataset will be stripped of patient identifiers prior to release for sharing. Because of the remote possibility of deductive disclosure of subjects' identities, we will make data available to interested parties under a data sharing agreement that includes commitments to the following: (a) use of data for research purposes only; (b) use of appropriate electronic safeguards to ensure information security; (c) destruction or return of the data after the analysis has been completed; (d) agreement to not use data for any commercial purposes; and (e) agreement to not redistribute the data to third parties. Interested parties will be able to request access to unpublished data from the Principal Investigators by email using the following contact information: [contact].

10.3 QUALITY ASSURANCE AND QUALITY CONTROL

10.3.1 Data Handling and Record Keeping

All study data will be maintained on HIPPA-compliant, secure servers through the University of Michigan Advanced Research Computing (ARC) core.

